Loss of uncollected distention medium onto the floor and into operating room blankets creates other hazards to the patient and surgical team besides the significant patient risks of fluid absorption. Fluid standing on the operating room floor can pose a fall risk to surgical team members (7). The effluent fluid from the patient that is not collected contains blood and bodily fluids that expose the surgical team to the hazards of infectious disease and biological toxins. Significantly, fluid becomes an electrical hazard when it comes into contact with electrical equipment. Distention medium that escapes capture may come in contact with electrical outlets, switches, and surgical electrodes increasing the risk of burns, fires and damage to equipment.

Additionally, the inaccurate detection of the fluid deficit may pose a clinical dilemma for the hysteroscopic surgeon. Does the surgeon stop a procedure when the fluid management alarm indicates that a fluid deficit (approximate patient fluid absorption) exceeds the safe limit even though they see fluid on the floor? If the surgery proceeds, how long can it safely continue? Without accurate, real-time fluid absorption data, surgeries may be prematurely terminated because of erroneously reported high fluid deficits thus requiring a potentially unnecessary repeat surgery with a delay in cure, increased cost, and more patient risks. The surgical team and healthcare system would certainly be exposed to medico-legal risk if a fluid management alarm sounds, the procedure is continued and the patient suffers a complication of fluid overload.

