### **III. Guideline Recommendations for Fluid management During Hysteroscopy**

Use of an automated fluid pump and monitoring system is advocated by both the American College of Obstetricians and Gynecologists and the American Association of Gynecologic Laparoscopists (8, 9). Guidelines for the threshold for acceptable fluid absorption by patients during hysteroscopy have been established by these groups. Most guidelines indicate that a threshold for safe absorption by patients is 500 to 750 mL for non-electrolytic media and 1000 mL for electrolytic medium such as normal saline. Data indicate that fluid absorption of greater than 1000 mL of electrolytic medium is associated with an increased risk of gas embolism (10). It has been shown with routine postoperative CT imaging of the brain that cerebral edema can occur with as little as 500 mL of non-electrolytic distension solutions (1). For other patients with cardiovascular disease or other comorbidities, the threshold for

safe absorption of medium should be reduced. An alarm can be set to sound a warning when a preset volume deficit is reached. Most operating rooms mandate a halt to the procedure following a warning alarm and, in some cases, special post-operative patient monitoring is required for patients to insure fluid and electrolyte normality, adequate pulmonary function, and hemodynamic stability.

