### Clinical Study Design

---

The primary outcome variable for the comparative trial will be the hysteroscopy fluid deficit (HFD) which can be precisely measured by the fluid management system by subtracting the outflow volume (OV) returned to the fluid management system from the inflow volume (IV). That is:

$$HFD = IV - OV$$

Secondary outcomes include uncollected fluid volume (UFV), occurrence of the alarm sounding for exceeding the fluid deficit limit, and procedure interruption. The UFV is defined as the difference of HFD between TCD and standard drape group. The UFV will be two components as determined by the circulating OR nurse in charge of the fluid management system. The first are the volume on the floor and the volume absorbed by the operation blankets and drapes. The second component is an estimate of any fluid loss from leaking hysteroscopy joints and gaskets not captured by the collection bag. In addition, the time required for procedures will be recorded.

Adverse events and serious adverse events will be captured along with relatedness and severity. We will classify event terms using Common Terminology Classification of Adverse Events version 4.03 (National Cancer Institute).

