#### **Measures for Drape Usability, Quality, and Convenience**

We plan to objectively and subjectively evaluate the usability and usefulness of the TCD compared to the standard drape. Staff will be asked to complete the System Usability Scale (SUS) [section XVII SUS; Brooke, 1986] to evaluate their perceived clinical usefulness of the TCD and the standard drape. The SUS is a validated 10-item survey for assessing perceived usability that uses a 5-point Likert scale ranging from strongly disagree to strongly agree. To further subjectively and objectively assess the TCD a human factors and design researcher will observe the surgeries. The human factors researcher will attend the first surgeries to ensure consistent rating with design researcher who will subsequently observe the remaining surgeries until data saturation is reached. The human factors expert will attend any surgeries the design researcher cannot attend. Staff will be asked to speak aloud using the system, which the researcher will record. Further, the researcher will complete an objective human factors assessment tool (section XVII). Finally, enrolled surgeons will be provided the opportunity to participate in one-on-one feedback sessions or focus group sessions to provide suggestions on how they perceive usability of the drape can be improved. These sessions will be facilitated by the Principal Investigator and the design researcher or human factors expert. These metrics will allow us to quantitate clinical usefulness and usability of both the operating surgeons and operating room staff. These results will not only provide this assessment of the TCD compared to the standard hysteroscopy drape (which is used across ORs within CHS) but will also provide important information to improve the drape if deficiencies are identified.

Adverse events and serious adverse events will be captured along with relatedness and severity. We will classify event terms using Common Terminology Classification of Adverse Events version 4.03 (National Cancer Institute).

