## **VI. Randomization and Blinding**

We will use standard randomization to allocate patients in a 1:1 allocation to the TCD or the standard hysteroscopy drape. The randomization lists will be generated by a study statistician within [name] team using SAS Enterprise Guide version 6.1. The assignments will be opaque envelopes which ensure allocation

concealment. Once a patient consents and is deemed eligible for the study, the study coordinator will provide the next envelope to the operation nurse who will open the envelope in privacy to learn the allocation. All study staff collecting and recording data for the trial will be masked to the drape that was used during the procedure.

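### The blanket claim that data collectors are masked to the drape cannot hold for nurse-determined uncollected fluid volume or the observer's usability tool

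*Combined protocol and SAP*

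**What the plan says.** Section VI (Randomization and Blinding) makes an unqualified statement: "All study staff collecting and recording data for the trial will be masked to the drape that was used during the procedure". Just before it, the coordinator hands the envelope to "the operation nurse who will open the envelope in privacy to learn the allocation".

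Other sections say where the data come from:

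- **UFV.** Clinical Study Design says: "The UFV will be two components as determined by the circulating OR nurse in charge of the fluid management system". The components are fluid on the floor and in the blankets and drapes, and an estimate of leakage from joints and gaskets. The same paragraph also defines UFV as the between-group difference in hysteroscopy fluid deficit (HFD). Section VIII lists estimated UFV from floor and blankets as a secondary outcome, to be analysed like the primary.
- **Usability.** Under Measures for Drape Usability, Quality, and Convenience, a human factors or design researcher observes the surgeries, and "the researcher will complete an objective human factors assessment tool".
- **Stopping and alarms.** Section VIII lists alarm occurrence and stopping for concern about overabsorption as secondary outcomes. Section III says "Most operating rooms mandate a halt to the procedure following a warning alarm" and "An alarm can be set to sound a warning when a preset volume deficit is reached". Section II instead describes a surgeon's dilemma when the indicated deficit "exceeds the safe limit even though they see fluid on the floor".
- **Adverse events.** "Adverse events and serious adverse events will be captured along with relatedness and severity". No assessor is named.
- **Primary outcome.** HFD is inflow minus outflow volume, computed by the fluid management system.

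**The concern.** The two drapes can be told apart by anyone in the room. Section IV describes the TCD as having a continuous plastic sheet above the collection bag, placed beneath the patient with the help of hand pouches. Someone who watches the drape in use, or judges how much fluid it has soaked up, knows which drape it is. The masking statement therefore fails for at least two sets of data.

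What is at stake is how the results are read. A report repeating section VI would present the nurse's UFV as a masked measurement, when it is partly an estimate made by someone who can see the drape and may hold a view about it. The observer's usability ratings are a milder case: rating a drape's usability is inherently unmasked, so there the sentence is wrong but the method is not.

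There is a related gap for the alarm outcome. The alarm is triggered by a device, but its limit is set by a person, and no section says whether that happens before or after the allocation is known.

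**Working it through.** No figure in the plan depends on masking, so the main check sets the sections side by side.

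| Data item | Source | Does the masking claim hold? |
|---|---|---|
| HFD (primary) | Fluid management system | Little room for judgement; masked transcription is possible but not described |
| UFV, nurse-determined | Circulating nurse, in the room | No, the estimate is unmasked |
| UFV, as HFD difference | Derived from system readings | As for HFD |
| Human factors tool | Researcher observing surgery | No |
| Alarm | Device, at a preset limit | Event yes; timing of the setting not stated |
| Stopping | Decision-maker and rule not stated | Cannot be determined |
| Adverse-event relatedness and severity | Assessor not stated | Cannot be determined |

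**The nurse.** The documents do not say whether the operation nurse who opens the envelope is the circulating nurse who determines UFV. It does not matter: whoever assesses fluid in the drapes sees the drape.

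**The researcher.** This person collects trial data under any ordinary meaning of study staff and watches the operation.

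**Data flow.** Section VII puts randomization, fluid measures and adverse events in the paper data collection. It describes no separation of allocation from outcome data, so masked data entry cannot be assumed.

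**Sensitivity of the UFV comparison.** Let S and T be mean UFV in the standard and TCD arms, and let the standard arm alone be misestimated by a proportion e. The estimated difference is (1 + e)S − T, so its relative shift is

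[(1 + e)S − T − (S − T)] / (S − T) = eS / (S − T).

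Inputs: section VIII's planning assumption that loss falls from 40% to 20% of inflow. Reading that loss as UFV is my assumption. The values of e are illustrative.

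- S = 40, T = 20, e = 0.10: 0.10 × 40 / 20 = 20% (difference 24 points instead of 20).
- S = 40, T = 20, e = 0.25: 0.25 × 40 / 20 = 50% (30 instead of 20).
- S = 40, T = 0, e = 0.10: 0.10 × 40 / 40 = 10%.

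The last case matches section VIII's equation, which has no UFV term for the TCD. But that equation describes the HFD difference. The nurse's UFV includes leaks from joints and gaskets, which belong to neither drape, so T need not be zero. A negative e gives the same sizes with the opposite sign.

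**The case against.** The strongest reply is that study staff means the research team, not hospital nurses. Section VI does distinguish the coordinator from the operation nurse, who opens the envelope in privacy. If the circulating nurse determines a volume that masked research staff then write down, the sentence could survive for UFV. That is a fair reading of the words, but the estimate itself would still be unmasked. Nor does it help with the observing researcher.

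A second reply is that Clinical Study Design defines UFV as the HFD difference, which the system supplies. That is true and belongs in the account. But the same paragraph has the nurse determine components, and section VIII plans to analyse an estimated UFV between arms. Two quantities share one name.

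A reader might go further and infer that stopping and adverse-event results are biased. The documents do not show this. Section III describes halts that most operating rooms mandate after an alarm, section II describes surgeon discretion, and neither is assigned to this trial. For adverse events the plan is silent on the assessor; silence is not a contradiction.

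A reader might also try to count how many changed stopping decisions would overturn a result. That count depends on the test. Take 34 per arm and the planned 50% versus 17%, about 17 versus 6. Three changes that narrow the gap give 17 versus 9 or 14 versus 6. Uncorrected chi-square gives p = 0.046 and 0.033; Fisher's exact test gives 0.080 and 0.061. Section VIII names chi-square for analysis and Fisher for power. With exposure itself unestablished, I place no weight on such counts.

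**Conclusion.** The masking sentence claims a property the design does not have. This is certain for the observer's tool and, whatever the nurse's staff status, for the nurse's UFV estimate. It is unresolved for stopping, for adverse-event relatedness and severity, and for when the alarm limit is set.

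The direction and size of any bias are unknown. The 20% shift for a 10% misestimate is a sensitivity figure. It assumes that the planning loss can be read as UFV and that only the standard arm is misestimated; it falls to 10% if the TCD loses nothing.

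The point does not undermine the main fluid-capture comparison. HFD is system-computed, and section VIII already treats its between-arm difference as the more accurate measure of UFV. HFD is not wholly immune: if stopping were decided by someone influenced by knowing the drape, duration and inflow could change and HFD with them. No section establishes that this happens. The sample size is unaffected. The correction should be made before results are known.

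**What to change.** 1. Replace the sentence in section VI with a statement, outcome by outcome, of who is masked and who is not.
2. State that nurse-determined UFV and observer usability ratings are unmasked, and label them so in the analysis and report.
3. Label stopping, and adverse-event relatedness and severity, as unmasked wherever the person judging them saw the drape.
4. Claim masking for HFD transcription, data entry or analysis only if it is actually arranged.
5. Give the nurse-determined volume and the HFD difference separate names, and keep the fluid-capture conclusion on system-computed HFD.
6. Record on the case report form, before the envelope is opened, the alarm limit set under usual site practice, without changing any clinical limit. Take alarm events from the device readout where available.

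The cost is protocol wording, one added form field and a small step in workflow order, since the limit must be written down before allocation is revealed. The trial also gives up its blanket claim of masked data collection. No added staff, patient procedure or change in sample size is needed.

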## VII. Data Management

Case report forms will be developed by the OBGYN clinical research nursing staff in collaboration with [name] and [name]. A REDCap database will be created for secure electronic data capture. The data flow will consist of paper data collection for eligibility assessment, baseline data, randomization, operational procedure, fluid measures, surgery outcomes, adverse events, and protocol deviations. The data will be entered into the electronic database within 3 business days of the enrollment.

## VIII. Statistical Methods and Sample Size Justification

The primary outcome for the study is the hysteroscopy fluid deficit (HFD) as determined by the fluid management system by subtracting the outflow volume (OV) from the inflow volume (IV) ( $HFD = IV - OV$ ). Our null hypothesis is  $H_0: \mu_{Standard} = \mu_{TCD}$  where  $\mu$ =mean fluid deficit. Our alternative hypothesis is  $H_a: \mu_{Standard} > \mu_{TCD}$  due to the underestimation of the outflow volume created by the loss of outflow fluid to floors and blankets. If we assume the true absorption rates by the patients are the same between the groups due to randomization, by estimating and testing the difference HFD between the two groups we are estimating and testing a more accurate measure of the uncollected fluid volume (UFV) as shown below:

$$\begin{aligned} \mu_{Standard} - \mu_{TCD} &= (\mu_{Standard, \text{true absorption}} + \mu_{Standard, \text{UFV}}) - \mu_{TCD, \text{true absorption}} \\ &= (\mu_{\text{true absorption}} + \mu_{Standard, \text{UFV}}) - \mu_{\text{true absorption}} \\ &= \mu_{Standard, \text{UFV}} \end{aligned}$$

The primary analysis for the study will use a general linear model on the HFD with a fixed effect for study group (TCD versus Standard drape) controlling for surgeon and indication for hysteroscopy, the stratification factors for the randomization.

Secondary outcomes include estimated uncollected fluid volume from floor and blankets, occurrence of the fluid deficit alarm sounding, stopping of the operation due to concerns of overabsorption by the patient, and adverse events. Estimated uncollected fluid volume will be analyzed similar to the primary outcome. All other outcomes are categorical and will be compared using Chi-square analyses.

We will sample 10 procedures (or until data saturation) from each arm (TCD vs standard) to conduct qualitative assessments on Usability using the Human Factors

Assessment Tool for the surgeons and operating team members. Once data saturation is reached using the Human Factors Assessment Tool, enrolled surgeons will be provided a step-by-step video link orientation to the Total Capture Drape. For the SUS, we will collect data on attending physicians only on their first and fifth procedures (the study team may change it to 1st and 3rd if deemed appropriate). We will estimate means or medians with standard deviations (or interquartile ranges) for the items and total scores for the SUS. Both within (1st vs. 5th) and between arms (TCD vs. standard) comparison on total scores of SUS will be conducted. We will compare the two groups using linear mixed models or generalized linear mixed models (depending on the distribution) with a random effect for the procedure to control for correlation of the measures among team members participating in the same procedure.

At this early stage of investigation, we have no prior data on HFD in patients to estimate the variability need for the sample size estimation. We have preliminary data from the simulated experiment showing a 100% recovering of loss deficit by the TCD. If we conservatively assume the loss deficit will decrease from 40% to 20% of the inflow volume, this would result in a clinically meaningful improvement with an approximate effect size of 0.92 based on the variability of loss deficit in the simulation. Given this, we are using effect size (relative to standard deviation) as the primary justification for the number of patients needed for the study. With a sample size of n=34 per arm, we would have 81% power to detect an effect size of 0.7 (0.7\*standard deviation of the HFD) with a two sided, two sample t-test ( $\alpha=0.05$ ). To account for potential missing data of 10%, we propose randomizing 76 women (n=38 per arm). With n=34 women in each group, we would also have 80% power to detect an absolute 33% reduction in the proportion of procedures with the alarm sounding due to fluid deficit threshold being reached assuming the proportion in the standard drape arm is 50%. This power was calculated using a Fisher's Exact test for testing proportions between two independent samples. The same power would apply for detecting differences in the proportion of procedures terminated.

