##### Standard Hysteroscopy Drape

[figure not shown]
[figure not shown]

Figure 1.

A proposed solution to the problem: The "Total Capture" Drape (TCD) for hysteroscopy prevents the escape of fluid that would otherwise not be measured by the standard drape because the TCD design includes a continuous sheet of non-permeable plastic that extends above the collection bag (see Figure 2 below).

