### **Data from Trial of Fluid Capture Efficiency of the TCD versus Conventional (Cardinal) Hysteroscopy Drape**

#### **General Observations**

A total of four trials per drape were conducted. The fluid loss (deficit) was calculated by subtracting the collected volume from the inflow volume by the fluid management system. This value should be 0 for all trials since the pelvic model was configured to have no absorption by the model and 100% of the fluid introduced would flow out of the artificial vagina. One trial from each product had procedural difficulties making results invalid. The first trial with the conventional hysteroscopy drape (Cardinal) was invalid because the pressure setting was too high (70 mm hg) instead of the standard 50

[figure not shown]

mm hg; the third trial of TCD was invalid because the saline bag became depleted in the middle of the trial.

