**"Total Capture" Drape Performance**

**Observations:**

- The Total Capture Drape did not rely on a skin-to-drape seal in order to function. With an extension flap underneath the patient, fluids running down the perineum were directed into the collection pouch and returned to the system.

- In four trials of the total capture drape, there was no deficit observed.

We concluded that no major design iterations would be required to move the TCD prototype to the next phase of development

**V. Comparative Trial for “Proof of Concept” Testing to Evaluate the Efficiency of the Total Capture Drape Compared to the Conventional Hysteroscopy Drape during Hysteroscopic Surgery**

All women undertaking hysteroscopy are required to have a sterile surgical drape with a fluid capture pouch system to collect the distention media not absorbed by the patient to calculate fluid deficits. Both the TCD and the standard hysteroscopy drape possess the characteristics described above, although design features of the standard drape are deficient. The TCD has received 510(k) FDA determination to be “substantially equivalent” to the standard hysteroscopy drape.

- a. **Subject Recruitment:** All women age 18 and older who are scheduled for an operative hysteroscopy at a CHS operating room facility are candidates for the trial. The research coordinator will be contacted by the physician of upcoming hysteroscopies. At that time, the coordinator will reach out to the patient to see if they are interested in participating. A consent will be emailed to the patient. Written consent will be obtained from patient in preop holding area.
- b. **Risks to the patient:** It will explain that the TCD may not perform in the same manner as the standard drape. It will be shared that the TCD will have met sterilization standards and that there is no evidence that the TCD would substantially alter the surgical risks of the hysteroscopy.
- c. **Exclusions:** Patients will be excluded if they are not acceptable candidates for a hysteroscopy procedure for any reason. Patients will be told that if they do not wish to participate in the trial that they will get the standard care that they normally would have received from their operating surgeon.
- d. **Benefits:** Patients will be told that the drape for surgical use may or may not improve surgical outcome. The information gained from the trial may provide benefit to others undergoing hysteroscopy in the future.

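### The primary fluid-deficit contrast estimates the reduction in uncollected fluid, not the standard drape's uncollected volume, and the name UFV is given to two different quantities

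*Combined protocol and SAP*

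**What the plan says.** The primary outcome is HFD, inflow volume minus the outflow volume returned to the fluid management system, by the same formula in both arms.

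Section VIII assumes equal true absorption in the two arms because of randomization, and says that by comparing HFD "we are estimating and testing a more accurate measure of the uncollected fluid volume (UFV) as shown below". The display that follows writes the standard arm's mean HFD as absorption plus UFV and the TCD arm's as absorption alone. It concludes that the difference equals the standard drape's mean UFV.

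Three other places bear on TCD loss:

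- Section IV says that the TCD "prevents the escape of fluid that would otherwise not be measured by the standard drape". It also reports that in the pelvic-model runs with the TCD "there was no deficit observed".
- The sample-size text in Section VIII cites "preliminary data from the simulated experiment showing a 100% recovering of loss deficit by the TCD", and then plans on less: "If we conservatively assume the loss deficit will decrease from 40% to 20% of the inflow volume".
- Section V, Clinical Study Design, says "The UFV is defined as the difference of HFD between TCD and standard drape group". Shortly afterwards it says "The UFV will be two components as determined by the circulating OR nurse in charge of the fluid management system". The components there are fluid on the floor, fluid in blankets and drapes, and leakage at hysteroscope joints and gaskets. Section VIII names only floor and blankets for the secondary outcome, and analyses it in the same way as HFD.

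**The concern.** HFD cannot tell absorbed fluid from fluid that was simply not returned. In either arm it is the sum of the two. Equal absorption cancels the first part of the sum and leaves any TCD loss in the contrast. Dropping that loss from the derivation assumes that the TCD captures everything.

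What is at stake is the meaning of the primary estimate. Section IV hypothesizes that the TCD records an accurate deficit in real time. The printed identity treats the TCD deficit as absorption by construction, so a positive result could be reported as support for accuracy when it shows only that the TCD loses less than the standard drape. Because Clinical Study Design defines the secondary outcome UFV as the same contrast, a report that follows the plan would also state the standard drape's loss too low whenever the TCD loses fluid.

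The double use of UFV adds to this. A between-group difference is one number for the whole trial and has no value for a single procedure. Only the nurse-determined volume can enter the linear model planned for UFV.

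**Working it through.** **The plan's own figures.** These reproduce.

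- Power: effect size 0.7, 34 per arm, two-sided two-sample t-test at 0.05. The noncentral t gives 81.2% (stated: 81%).
- Number randomized: 34 / 0.90 = 37.8, rounded up to 38 per arm, 76 in total (stated: 76).
- Effect size 0.92: mean inflow over the six tabulated pelvic-model runs is (1250 + 862 + 1260 + 1255 + 1059 + 1131) / 6 = 1136 mL, and 20% of that is 227 mL. The SD of the standard-drape losses (340, 482, 820 mL) is 246.6 mL. 227 / 246.6 = 0.92.

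**The identity.** Let A be mean absorption, equal in both arms by the plan's assumption, S the standard drape's mean uncollected volume and T the TCD's.

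- Mean HFD, standard: A + S
- Mean HFD, TCD: A + T
- Difference: (A + S) − (A + T) = S − T

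The plan prints S, which is correct only if T = 0. The ratio of the contrast to the quantity it is said to estimate is (S − T) / S.

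**Size, if 40% is uncollected fluid.** The documents give no TCD loss in patients, so T is an assumed range. S = 40% of inflow.

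| T, % of inflow | S − T, % of inflow | (S − T) / S |
|---|---|---|
| 0 | 40 | 1.00 |
| 5 | 35 | 0.875 |
| 10 | 30 | 0.75 |
| 20 | 20 | 0.50 |

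The last row takes the plan's 20% as TCD loss. At the pelvic-model mean inflow this is 227 mL against 454 mL. Those volumes come from 60-second runs and serve only as illustration; the ratio does not depend on them.

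**Size, if 40% and 20% are total HFD.** With absorption a (% of inflow, assumed), S = 40 − a and T = 20 − a, so the ratio is 20 / (40 − a).

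| a, % of inflow | 0 | 5 | 10 | 15 | 20 |
|---|---|---|---|---|---|
| Ratio | 0.50 | 0.57 | 0.67 | 0.80 | 1.00 |

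The printed identity then holds only if absorption accounts for the whole 20%.

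**Which reading is likelier.** The 0.92 rests on the SD of losses in a bench test where "the pelvic model was configured to have no absorption by the model", so deficit there was entirely uncollected fluid. That favours the first reading without settling it.

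**Joint and gasket leakage.** If it counts as UFV, as in Clinical Study Design, a leak L equal in both arms cancels from the contrast but stays in S. With S = 40% including L and no other TCD loss, the ratio is (40 − L) / 40: 0.95 at L = 2%, 0.875 at L = 5% (both assumed). If UFV means floor and blankets only, as in Section VIII, this does not arise.

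**The two uses of UFV.** If the nurse-determined volumes are accurate, their mean difference between arms is also S − T. The two uses therefore agree on the value of the contrast. They conflict in meaning: one is a group contrast, the other a volume for one procedure.

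**The case against.** The strongest reply is that this is a slip in an explanatory derivation. The hypotheses concern mean HFD. No decision rule, sample-size input or safety limit uses the absolute size of the standard drape's UFV. The zero-loss premise can be seen in the first displayed line, it is what the drape is designed to achieve, and the pelvic-model runs support it. Section VIII also speaks of estimated UFV for the secondary outcome, so an analyst would know which variable to model.

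Much of this stands. The premise is visible, though never put in words, and the analysis is sound. But the support is three tabulated runs in a non-absorbing model, with nothing from patients. And because Clinical Study Design makes the contrast the definition of a secondary outcome, the slip would carry into a reported result.

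A reader might infer more than the documents support, in four ways:

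- *That the primary test or sample size is invalid.* It is not. Both rest on the standardized HFD difference, whatever that difference is called.
- *That Section VIII asserts a 20% TCD loss and so flatly contradicts zero loss.* The 40%-to-20% fall is offered as a conservative planning figure, may refer to total HFD, and is not the basis of the final number, which uses 0.7 SD. It sits badly with zero loss; no more can be said.
- *That shared joint leakage defeats the identity on any reading.* It does so only under the wider component list.
- *That a bias of known size has been shown.* Every ratio above rests on an assumed loss, absorption or leak.

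**Conclusion.** The point holds and should be fixed. As printed, the identity is correct only if the TCD loses no fluid. Under the plan's one verbal assumption, equal absorption, the HFD contrast is the reduction in uncollected fluid. It falls short of the standard drape's UFV by exactly the TCD's own loss: to 50% of it if the planning figures of 40% and 20% are both uncollected fluid, and to between 50% and 100% if they are total HFD with absorption anywhere from 0 to 20% of inflow.

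A positive result would show that the TCD loses less fluid. It would not show that it loses none, or that its deficit equals absorption. The two meanings of UFV and the differing component lists are a second, smaller inconsistency in wording.

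**What to change.** 1. Section VIII: add the TCD's UFV to the derivation, so that the last line is the standard drape's mean UFV minus the TCD's.
2. Describe the primary result as the reduction in uncollected fluid, not as the standard drape's UFV or as evidence that the TCD deficit equals absorption.
3. Section V, Clinical Study Design: give the HFD contrast its own name, for example reduction in uncollected fluid, and keep UFV for the nurse-determined volume of each procedure.
4. Use one component list in both sections. State whether drapes and joint or gasket leakage belong to UFV.
5. Report mean estimated UFV in each arm, including the TCD arm, with a 95% confidence interval, as supportive evidence only, since it is an estimate. At 34 per arm the half-width is about 2.03 / √34 = 0.35 SD.

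The cost is wording in two sections and one summary per arm, from volumes that the planned UFV model already needs in both arms. The test, model, power and sample size stay as they are. The price is a narrower claim: a reduction in loss rather than full accuracy.
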